### 7.5.1 Best Overall Response, Objective Response Rate, Clinical Benefit Rate

BOR will be summarized by response category. Number and percentage of subjects who achieved CR, or PR (ORR) and who achieved CR, PR or SD (CBR) will be summarized with 95% CIs.

### 7.5.2 Duration of Response and Time to Response

The DOR will be summarized for subjects who achieve confirmed PR or better determined by investigators. Median and 95% CI for DOR among responders will be estimated. The quartiles

(25%, median, and 75%) of DOR and 95% CI for median DOR will be provided by Kaplan-Meier method. Along with DOR statistics, the number and percentage of subjects who have events or censored will also be presented. Among the responders, subjects who remain alive and have not progressed are continued responders and are censored on the last evaluable disease assessment date (prior to subsequent cancer therapy). The number and percentage of continued responders will be presented. Summary statistics of TTR will also be provided for responders. A listing instead of summary tables may be provided for DOR and TTR if there are not sufficiently large number of confirmed responders.

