### **5.2.3.1 Criteria for Discontinuation from Treatment**

Study treatment may be discontinued for any of the following reasons:

- Any clinical AE, laboratory abnormality, or intercurrent illness that would, in the judgment of the Investigator, affect assessments of clinical status to a significant degree
- Toxicity that, despite maximum medical management, in the judgment of the Investigator, compromises the ability to continue study-specific procedures or is considered to not be in the patient's best interest
- Disease progression (based on Investigator assessment of baseline and post-baseline scans as per RECIST 1.1). In some circumstances patients may be treated beyond disease progression. Details are provided in Section [5.2.5](#).
- Patient request to discontinue treatment for any reason
- Patient noncompliance
- Initiation of systemic antineoplastic therapy other than treatments per protocol in the absence of progression
- Discontinuation of the study treatment at the request of Nektar, a regulatory agency or an institutional review board (IRB) or independent ethics committee (IEC)
- Pregnancy during treatment
- Death
- Investigator's decision, in consultation with the Medical Monitor

If a patient discontinues NKTR-255, the patient may continue on cetuximab alone, at the discretion of the Investigator, until disease progression or initiation of systemic anti-tumor therapy (whichever is earlier).

If a patient discontinues study drug(s), every attempt should be made to continue tumor assessment at every 9 weeks until disease progression or initiation of systemic anti-tumor therapy. The patient will be asked to attend the 60-day post-treatment follow-up assessment visit when discontinuing from the study treatment.

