### **5.2.3.3 Criteria for Discontinuation from Study**

Patients who discontinue study treatment due to any of the treatment discontinuation criteria in Section 5.2.3.1 will continue to be followed for survival per Section 5.2.7.

In the event of an unscheduled study termination by the Sponsor, patients who are on-treatment at the time of the end of the study will be followed for safety for 60 days post EOT as per Section 5.2.6.

Criteria for study discontinuation may include:

- Withdrawal of consent from study
- Loss to follow-up
- Death
- Discontinuation of the study at the request of Nektar, a regulatory agency or an IRB/IEC
- Principal Investigator's decision
- Medical Monitor's assessment due to lack of adherence to protocol

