**Treatment-emergent adverse events (TEAE):**

- Any AE that occurs after study treatment initiation.
- An AE that was present at the time of study treatment initiation but worsened after study treatment initiation.
- An AE that was present and resolved prior to treatment and reappeared after treatment initiation.
- Any treatment-related AE will always be considered treatment-emergent.

**NKTR-255 Treatment-emergent adverse events (TEAE) period:** Start of NKTR-255 through 30 days post last dose NKTR-255, or until a new antineoplastic regimen has been initiated, whichever comes first.

**Extended treatment-emergent adverse events (TEAE) period:** Start of any study drug through 60 days post last dose of study drug, or until a new antineoplastic regimen has been initiated, whichever comes first.

**Prior medications:** Prior medications are defined as medications with start date prior to C1D1.

**Concomitant medications:** Concomitant medications are defined as medications with stop date after C1D1, or medications with start date on or after C1D1 and up to 30 days after the last dose of NKTR-255. Medications with a start date after the initiation of any subsequent anticancer treatment will not be considered concomitant medications.

Medications with start date prior to C1D1 and end date after C1D1 will be classified as both prior and concomitant medications.

**Best overall response (BOR):** The BOR is defined as the confirmed best response designation over post-baseline response assessments. Disease assessments beyond progression or after start of subsequent therapy will not be considered for BOR.

**Overall response rate (ORR):** The ORR is defined as the proportion of subjects who have achieved PR or better as their BOR.

**Complete response rate (CRR):** The CRR is defined as the proportion of subjects who have achieved CR as their BOR.

**Responders:** Responders are defined as subjects with a confirmed BOR of PR or better. Ongoing responders are defined as responders who have not progressed, not died, not been off study and not started a subsequent therapy.

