**Duration of response (DOR):** DOR is defined as the time from first response (PR or better) to the date of disease progression or death due to any cause, whichever occurs first. Subjects who remain alive and have not progressed are censored on the last evaluable disease assessment date (prior to subsequent cancer therapy). Same censoring rules for PFS apply to DOR. This endpoint is only defined for subjects with a confirmed BOR of PR or better.

**Time to response (TTR):** TTR is defined as the time from treatment start date (i.e. first dose of Cetuximab) to first response (PR or better). This endpoint is only applied for subjects with a confirmed BOR of PR or better.

**Progression free survival (PFS):** The PFS is defined as the time between the first dose date of Cetuximab to the date of disease progression or death, whichever is earlier. For patients without PD or death, those patients will be censored following the rules specified below.

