**Table 3: PFS Censoring Rules**

Situation	Date of Disease Progression or Censoring	Outcome
No post-baseline tumor assessments and no death	first dose date of Cetuximab	Censored
No progression and no death, and no new anti-cancer therapy started	Date of last assessment showing no evidence of disease progression	Censored
New anti-cancer therapy started without progression before	Date of last assessment before the start of anti-cancer therapy showing no evidence of disease progression	Censored
Disease progression reported on one or multiple response assessments without new anti-cancer therapy before	Date of earliest evidence of PD	Progressed
Death without PD or new anti-cancer therapy before	Date of death	Death
Two or more consecutive missing tumor assessments, and no progression before the missing assessment	Date of the last assessment prior to the missing assessment showing no evidence of disease progression	Censored

**Overall Survival (OS):** OS is defined as the time from the first dose date of Cetuximab to death from any cause. Patients will be followed until their date of death, loss to follow-up, or withdrawal of consent for further follow-up for survival, regardless of the start of anti-cancer therapy. Patients who are lost to follow-up will be censored at their last date known to be alive. Patients who do not have date of death at data cut-off date will be censored at their last date known to be alive. Patients who do not have any follow-up since first dose date of Cetuximab will be censored on the first dose date of Cetuximab.

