## 7.5 Efficacy Analysis

Tumor response will be evaluated using RECIST 1.1 criteria ([Eisenhauer, 2009](#)). Tumor burden will be characterized prior to enrollment, and response assessments will be at approximately every 9 weeks starting from C1D1. A confirmed BOR of CR or PR requires the confirmation occurring at least 4 weeks after initial documentation. A BOR of SD requires a minimum of 63 days on study from C1D1 to the date of the first imaging assessment., Disease assessment at both scheduled and unscheduled visits will be used for efficacy endpoints. Disease assessments after new systemic anti-cancer therapy, surgical procedures or radiotherapy on target lesions will be excluded. Treatment beyond progression is allowed for qualified subjects. However, tumor assessment beyond progression will not be considered for response endpoints.

For efficacy endpoints including ORR, CBR, BOR summary will be based on the response-evaluable population. DOR and TTR will be summarized among confirmed responders. PFS, OS will be analyzed in the safety population. In addition, swimmer plot of tumor response and waterfall plot of best tumor size change will be generated based on safety population. Separate summary table and figures for efficacy analyses will be generated for HNSCC and CRC patients.

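### SAP 6.6.1 and SAP 7.5.2 define responders still in response differently, and the looser 7.5.2 definition is the one attached to the reported count

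*SAP*

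**What the plan says.** SAP 6.6.1, in the entry on responders, reads: "Ongoing responders are defined as responders who have not progressed, not died, not been off study and not started a subsequent therapy". The term *ongoing responders* is not used again in the visible SAP text.

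SAP 7.5.2, on duration of response, uses another term and a shorter test: "subjects who remain alive and have not progressed are continued responders and are censored on the last evaluable disease assessment date". A parenthesis then says that the assessment used for censoring must precede any subsequent cancer therapy. The reported result follows: "The number and percentage of continued responders will be presented". The same section also reports how many responders had events and how many were censored. It allows a listing in place of the DOR and time-to-response tables if confirmed responders are too few.

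On censoring, SAP 6.6.1 states: "Same censoring rules for PFS apply to DOR". SAP Table 3 treats the situation "New anti-cancer therapy started without progression before" as censored. SAP section 12, which lists changes from the protocol, does not mention continued or ongoing responders.

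**The concern.** The share of responders still in response is read beside median DOR as a measure of durability. A reader will take it to mean patients who were still being followed, still in response and not on another treatment. That is what 6.6.1 describes. 7.5.2 drops the last two conditions, and it is the section that specifies the output.

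Two programmers, each following one of these sections, could therefore produce different numbers from the same data. Under the looser rule, a switch to another therapy, or possibly departure from the study, would be presented as continued response. The looser count also adds little, because 7.5.2 already reports the number censored. Only the stricter definition separates patients still observed in response from those censored for other reasons.

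**Working it through.** The plan states no figure that depends on this point, so there is none to reproduce. The check compares the two definitions for each status that a confirmed responder can have.

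| Status of confirmed responder | SAP 6.6.1 *ongoing* | SAP 7.5.2 *continued* |
|---|---|---|
| (a) Alive, unprogressed, on study, no new therapy | counted | counted |
| (b) Alive, unprogressed, started new anti-cancer therapy | not counted | counted |
| (c) Unprogressed, not known to have died, withdrew or lost to follow-up | not counted | arguably counted |
| (d) Progressed or died | not counted | not counted |

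The definitions part only in (b) and (c).

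**Case (b).** The parenthesis in 7.5.2 fixes which assessment supplies the censoring date. It does not remove the patient from the group; it presupposes that some members have gone on to other therapy. Such a patient would normally remain unprogressed for this analysis, for two reasons:

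- SAP 7.5 says: "Disease assessments after new systemic anti-cancer therapy, surgical procedures or radiotherapy on target lesions will be excluded".
- Protocol 5.2.3.1 asks for scans after treatment stops only up to a point: "every attempt should be made to continue tumor assessment at every 9 weeks until disease progression or initiation of systemic anti-tumor therapy".

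The same protocol section lists the start of another systemic cancer treatment in the absence of progression as a reason to stop study treatment, so the plan foresees these patients.

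**Case (c).** Protocol 5.2.3.3 lists "Withdrawal of consent from study" and loss to follow-up among the criteria for leaving the study. Whether such a patient meets the requirement in 7.5.2 to remain alive is a matter of interpretation, so this case is less certain than (b).

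**Size.** The inputs are about 30 Phase 1b patients (Protocol 5.1.1, SAP 5.0) and an assumed confirmed response rate of 10% to 20%. The rate is an assumption.

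- Responders: 0.10 × 30 = 3 to 0.20 × 30 = 6.
- Shift per patient in (b) or (c): 1/3 = 33 points to 1/6 = 17 points.
- Illustration with 6 responders: 2 in (a), 2 in (b) or (c), 2 in (d). SAP 6.6.1 gives 2/6 = 33%. SAP 7.5.2 gives (2 + 2)/6 = 67%.
- With nobody in (b) or (c), the shift is 0.

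SAP 7.5 also calls for separate HNSCC and CRC efficacy summaries, so a denominator may be smaller than these.

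**Continued against censored.** Table 3 makes death an event only if neither progression nor new therapy came first. A responder who starts new therapy and then dies is therefore censored but not alive. A responder who misses two or more consecutive assessments and then progresses or dies is also censored, but is not both alive and unprogressed. Continued responders under 7.5.2 are thus a subset of the censored responders, and the two percentages need not agree.

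**The case against.** The case against giving this much weight has several parts.

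- **The labels differ.** 6.6.1 says *ongoing* and 7.5.2 says *continued*, so they could be two concepts. That is possible, but no visible text gives them different meanings, and the natural reading is one idea defined twice.
- **The effect is conditional.** It needs 7.5.2 to be programmed literally and at least one affected patient to exist. This stands. A reader might infer that the reported count will include patients no longer observed in response; the documents support only that it would, under those conditions.
- **The percentage may never be tabulated.** With few responders, the listing option in 7.5.2 could apply. This stands, but the option is discretionary, and any response-status flag in a listing would need the same definition.
- **Other outputs help.** The censored count, the swimmer plot, the listing of subsequent therapy and the disposition listing would let a careful reader find who switched or left. This reduces the harm but does not settle the definition.
- **Little rests on the count.** It is descriptive. The Phase 1b primary endpoints are DLTs and treatment-emergent adverse events, and no test or dose decision uses it. This stands and limits the severity.
- **The 6.6.1 wording has its own flaw.** Protocol 5.2.3.3 includes discontinuation of the study at the sponsor's request, and Protocol 5.2.8 lets a sponsor decision end the study. Read literally, the off-study condition could then exclude patients still in response at closure. This stands, and the fix has to deal with it.

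**Conclusion.** The inconsistency is real, and its importance is minor. 7.5.2 attaches the reported number and percentage to a two-condition definition, 6.6.1 gives a four-condition one, and nothing says which applies. The clear discrepancy concerns living responders who started new therapy without progression. For patients who withdrew or were lost to follow-up it is arguable. The shift of 17 to 33 points per affected patient rests on an assumed 3 to 6 responders and is zero if there are no such patients.

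Two stronger readings are tempting but unsupported. One is that the continued-responder percentage equals the percentage censored for any reason; Table 3 shows that it need not. The other is that the DOR analysis itself is distorted; the censoring rule does not depend on the label, so the Kaplan-Meier estimate is the same under either definition.

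**What to change.** Use one term and one definition in SAP 6.6.1 and 7.5.2. Count as a continued responder only a confirmed responder with none of the following before data cut-off: progression, death, subsequent anti-cancer therapy, withdrawal or loss to follow-up. State that closure of the study by the sponsor does not by itself make a responder off study. Show the other censored responders by censoring reason, and use the same definition for any flag in a listing that replaces the table.

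The cost is a sentence or two in the SAP and slightly more tabulation. The continued-response percentage may come out less favourable. No data collection and no Kaplan-Meier analysis changes.

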### **7.5.3 Progression Free Survival (PFS)**

PFS will be analyzed in the safety population. Investigator-assessed PFS will be summarized descriptively using the Kaplan-Meier (KM) product-limit method. KM estimate of PFS rates at 6, 9 and 12 months will be calculated. PFS rates at 18, and 24 months may also be estimated depending on whether minimum follow-up will be longer than timepoint to generate the rate. Quartiles (25%, median and 95% confidence interval, and 75%) of PFS, along with two-sided 95% CIs (based on the log-log transformation) for median PFS will be calculated. The reasons of PFS events (death vs. progression) will be summarized. PFS KM curve will be plotted.

### **7.5.4 Overall Survival**

OS will be analyzed in the safety population. OS will be summarized descriptively using the Kaplan-Meier (KM) product-limit method. KM estimate of OS rates at 6, 9 and 12 months will be calculated. OS rates at 18, and 24 months may also be estimated depending on whether minimum follow-up will be longer than timepoint to generate the rate. Quartiles (25%, median and 95% confidence interval, and 75%) of OS, along with two-sided 95% CIs (based on the log-log transformation) of median OS, will be calculated. OS KM curve will be plotted.

### **7.5.5 Subgroup Analysis**

No subgroup analysis is planned for efficacy endpoints other than summarizing separately for HNSCC and CRC patients.

## **7.6 Safety Analyses**

Unless otherwise specified, all safety analyses except for incidence of DLTs will be based on the Safety Population. All summaries will be provided by dose groups in Phase 1b.

### **7.6.1 Dose Limiting Toxicities**

DLTs will be evaluated in the DLT evaluation window of 21 days following NKTR-255 administration in Cycle 1 Day 1 as specified in the protocol. Delayed DLTs are AEs that meet criteria of DLT defined in the protocol but occur after the DLT evaluation window. DLTs and delayed DLTs will be summarized separately by system organ class (SOC) and preferred term (PT) in the DLT population. All DLTs and delay DLTs will be listed by patient.

## 7.6.2 Adverse Events

Verbatim AE terms on case report forms will be mapped to PTs and SOCs using the Medical Dictionary for Regulatory Activities (MedDRA) (version 22.0). CRS events are graded based upon ASBMT 2018 criteria. All other Adverse Events and toxicity will be evaluated according to CTCAE Version 5.0.

TEAEs will be summarized by SOC, PT, CTCAE grade of severity, and relationship to the study treatment. For patient level summaries, patients with multiple occurrences of events of the same PT and SOC will be counted once.

TEAE period defined in Section 6.6.1 will be applied if AEs are summarized in safety population, extended TEAE period will be applied if AEs are summarized in enrolled population. All AE tables by worst CTCAE grade will include 4 categories, which are Grade 1-2, Grade 3-4, Grade 5 and all Grades.

The following AE summaries will be provided in safety population with NKTR-255 TEAE period

- Overall summary of TEAEs
- TEAEs by SOC, PT and Worst CTC Grade
- Grade 3 and above TEAEs by SOC and PT
- TEAE Related to NKTR-255 by SOC, PT and Worst CTC Grade
- Serious TEAE by SOC, PT and Worst CTC Grade
- Serious TEAE Related to NKTR-255 by SOC, PT and Worst CTC Grade
- Grade 3 and above TEAEs related to NKTR-255 by SOC and PT
- TEAE Leading to NKTR-255 Dose Delay by SOC and PT
- TEAE Leading to NKTR-255 Dose Reduction by SOC and PT
- TEAE Leading to NKTR-255 Dose Interruption by SOC and PT
- TEAE Leading to Discontinuation of NKTR-255 by SOC and PT
- TEAE Leading to Death by SOC and PT

Other safety observations (OSO) will be summarized in following categories:

- AEs associated with increased cytokine levels in blood
  - Arthralgia
  - Asthenic conditions/Fatigue
  - Flu like symptoms

- Elevated hepatic transaminases
- Hypotension
- Rash and pruritus
- Cytokine release syndrome (CRS)
- Elevated hepatic transaminase
- ICANs (this is an individual PT which is Immune Effector Cell-Associated Neurotoxicity Syndrome and is included in TEAE summary tables)
- Infections
- Infusion related reaction (IRR, 48-hour window post NKTR-255 administration)
- Neutropenia
- QT/QTc Prolongation
- Thrombocytopenia

For IRR (except for the PT of infusion related reaction), events that start within 48 hours after NKTR-255 drug administration will be included. If AE onset time is available, the time information will be used to exclude events that start before dosing and include events that start on day 3 relative to dosing day but within 48 hours of start of NKTR-255 administration; otherwise, AEs that start on the same and next day of dosing will be included. Analysis on IRR will only be performed for patients who receive at least one NKTR-255 dose.

The following summaries will be performed for OSO using safety population with TEAE period. A listing of how OSO is categorized will also be provided.

- Treatment-emergent Other Safety Observations (OSO) by Category/PT and Worst CTC Grade
- Grade 3 and above Treatment-emergent Other Safety Observations (OSO) by Category/PT
- Treatment-emergent Other Safety Observations (OSO) Related to NKTR-255 by Category/PT and Worst CTC Grade
- Serious Treatment-emergent Other Safety Observations (OSO) by Category/PT and Worst CTC Grade
- Serious Treatment-emergent Other Safety Observations (OSO) Related to NKTR-255 by Category/PT and Worst CTC Grade

Additionally, site identified Treatment-emergent CRS events will also be summarized and listed by PT and Worst CTC Grade.

The following AE summaries will be provided in enrolled population with extended TEAE period:

- Overall summary of Extended TEAEs
- Extended TEAE Related to any Study Drug by SOC, PT and Worst CTC Grade
- Serious Extended TEAE Related to any Study Drug by SOC, PT and Worst CTC Grade
- Grade 3 and above Extended TEAEs related to any Study Drug by SOC and PT
- Extended TEAE Leading to Discontinuation of any Study Drug by SOC and PT
- Extended TEAE Leading to death by SOC and PT

The following data listings will be provided in enrolled population:

- All TEAEs
- Serious TEAEs
- Grade 3 or Higher TEAEs
- Other Safety Observations (OSO)
- TEAEs Leading to Study Drug Discontinuation
- TEAEs Leading to Dose delay, Reduction, and Interruption
- TEAE leading to death

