Study Population:	Adults at least 18 years of age having R/R cancer of one of the following tumor types: 

• HNSCC

• CRC

Number of Patients (planned):	Phase 1b Dose Escalation: Approximately 30 patients Phase 2 Dose Expansion: CCI
Number of Study Sites:	CCI
Countries:	United States (US) and rest of world
Study Design:	This study is a Phase 1b/2, open-label, multicenter, dose escalation, and dose expansion study in patients with R/R HNSCC, CRC CCI Phase 1b – Dose Escalation 

• The NKTR-255 starting dose will be 1.5 <math>\mu</math>g/kg IV, which had no safety concerns as defined by pre-specified dose-limiting toxicities in the first cohort of the ongoing first-in-human (FIH) study Protocol 18-255-02. The starting dose is based on ongoing safety data generated from the escalation cohorts and the RP2D determination from the FIH study. The starting dose will not be greater than the highest dose determined by the Safety Review Committee (SRC) to have no safety concerns in the FIH study.

• After an initial cetuximab loading dose of 400 mg/m^2 IV during the study run-in period (Day -7), patients will receive IV NKTR-255 every 21 days (q21d) in combination with 250 mg/m^2 IV cetuximab weekly. On days that NKTR-255 and cetuximab are both dosed, cetuximab should be administered first, followed by NKTR-255 a minimum of 1 hour later but within 3 hours of completing the cetuximab infusion.

 
Beginning with Dose Level 1, successive dose levels of at least 3 patients will receive ascending doses of NKTR-255 until the MTD and/or RP2D is determined. Approximately 30 patients will be enrolled in the dose escalation phase of the study. A 2-parameter Bayesian logistic regression model (BLRM) employing the escalation with overdose control (EWOC) principle (Neuenschwander, 2008) will be used as a guide during the escalation phase of the study for dose level selection and for determination of the MTD and/or RP2D. Additional groups may also be opened to further explore the MTD. For details, refer to Sections 5.1, 5.8, and 5.9.

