### 2.2.6.1 Safety Considerations for NKTR-255 and Cetuximab Combination

Cetuximab is a targeted monoclonal antibody to EGFR and has been part of the treatment backbone for metastatic CRC since its approval in 2004 and for HNSCC since approval in 2006. The safety of cetuximab as monotherapy has been well characterized and summarized by several multicenter clinical studies ([Fakih, 2010](#); [Erbitux US package insert, 2021](#)). In this study, the loading dose of cetuximab will be given as monotherapy.

Infusion-related reactions occurred within minutes of administration of cetuximab (median: 15 minutes, range: 2 to 140 minutes). The time from start of cetuximab to onset of IRR correlated inversely with the grade of the IRR, whereby the onset of the IRR occurred much earlier with Grade 4 IRR and later with lower grades of IRR (median to onset of Grades 4, 3, 2, and 1 IRR were 5, 13.5, 22, and 25 minutes, respectively,  $p = 0.04$ ). Pharmacologic prophylaxis with antihistamines IV 30 to 60 minutes prior to the first dose has been shown to be effective in reducing IRR incidence ([Touma, 2014](#)).

CCI

CCI

CCI

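### SAP 7.6.2 defines the infusion-reaction category by a 48-hour window after NKTR-255 but exempts the preferred term 'infusion related reaction', so cetuximab reactions outside that window are counted in it

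*SAP*

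**What the plan says.** SAP 7.6.2 (Adverse Events) gives the category as "Infusion related reaction (IRR, 48-hour window post NKTR-255 administration". The counting rule later in the same section is "For IRR (except for the PT of infusion related reaction), events that start within 48 hours after NKTR-255 drug administration will be included". For the terms under the window, a recorded onset time is used to "exclude events that start before dosing and include events that start on day 3 relative to dosing day", provided the event is still within 48 hours. Without an onset time the fallback is: "otherwise, AEs that start on the same and next day of dosing will be included".

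On population and period, "The following summaries will be performed for OSO using safety population with TEAE period", and "TEAE period defined in Section 6.6.1 will be applied if AEs are summarized in safety population". SAP 6.6.1 opens the NKTR-255 period at the start of NKTR-255. It closes 30 days after the last NKTR-255 dose, or earlier if a new antineoplastic regimen begins. The section also limits the IRR analysis to patients given NKTR-255 at least once; that restricts patients, not the timing of events.

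On the schedule, Protocol 5.1.1 gives NKTR-255 every 21 days and cetuximab weekly after a Day -7 loading dose. On shared days, the Protocol synopsis says, "cetuximab should be administered first, followed by NKTR-255 a minimum of 1 hour later" and at most 3 hours after the cetuximab infusion ends. On cetuximab's own reactions, Protocol 2.2.6.1 states: "Infusion-related reactions occurred within minutes of administration of cetuximab (median: 15 minutes, range: 2 to 140 minutes".

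**The concern.** The category description and the counting rule disagree about the term most specific to the event. Non-specific terms must start within 48 hours of NKTR-255. The diagnosis itself counts at any time in the treatment-emergent period.

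With a single infused drug this might be harmless. Phase 1b, the only part the SAP analyses, infuses two, and the more frequently infused one is known to cause these reactions. A reaction to cetuximab on Day 8 or Day 15 would be tabulated in a category the SAP defines by its timing after NKTR-255.

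Of the five planned summaries of other safety observations, three (all, Grade 3 and above, serious) have no causality filter, and those three are affected. The two restricted to NKTR-255-related events depend wholly on the investigator's attribution. At stake is how a reader interprets one named safety observation for NKTR-255: the timing that could help separate the two drugs is withheld from the key term.

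**Working it through.** The plan states no figure to reproduce. The check applies the SAP's timing rules to the planned schedule and asks which cetuximab infusions could produce a reaction that is counted.

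**Inputs**
- Cetuximab on Day -7, then Days 1, 8 and 15 of each 21-day cycle; NKTR-255 on Day 1 (Protocol 5.1.1 and Table 1).
- Shared days: NKTR-255 starts 1 to 3 hours after the cetuximab infusion ends (Protocol synopsis).
- Reaction onset at the quoted median of 15 minutes (Protocol 2.2.6.1).
- Counting period: first NKTR-255 dose to 30 days after the last (SAP 6.6.1).
- Assumptions: no missed doses, no new regimen, and cetuximab starting 2 hours before NKTR-255 on shared days. The 2 hours are not critical: cetuximab always starts more than 1 hour before NKTR-255, so a 15-minute reaction comes first in any case.

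**Step 1: cetuximab-only days.** Days 8 and 15 are 7 × 24 = 168 and 14 × 24 = 336 hours after NKTR-255. Both are outside 48 hours but inside the counting period. In the last cycle they fall 7 and 14 days after the final NKTR-255 dose, within the 30 days. For c cycles this gives 2c infusions.

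**Step 2: shared days.** A reaction before that day's NKTR-255 is about 21 days after the previous dose, so it is outside every 48-hour window. From Cycle 2 on it is inside the counting period. This gives c − 1 infusions.

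**Step 3: infusions not counted.** The Day -7 load and the Cycle 1 Day 1 cetuximab infusion precede the first NKTR-255 dose and so the period: 2 infusions.

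**Step 4: totals.** Planned infusions = 1 + 3c. Counted = 2c + (c − 1) = 3c − 1.

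| Cycles | Planned | Cetuximab-only days | Shared day, before NKTR-255 | Counted | Counted if the window applied and onset times were recorded |
|---|---|---|---|---|---|
| 1 | 4 | 2 | 0 | 2 | 0 |
| 2 | 7 | 4 | 1 | 5 | 0 |
| 3 | 10 | 6 | 2 | 8 | 0 |
| 4 | 13 | 8 | 3 | 11 | 0 |

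Protocol 5.2.3.1 lets a patient who stops NKTR-255 continue cetuximab alone. Weekly doses 21 and 28 days after the last NKTR-255 dose would add up to 2 more infusions inside the 30 days; they are not in the table.

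**Step 5: limit of the window.** The zeros hold for reactions at the median onset. The quoted range runs to 140 minutes. With the minimum 60-minute gap, a 140-minute reaction would start after NKTR-255 if the cetuximab infusion lasted less than 140 − 60 = 80 minutes. The window therefore cannot fully separate the drugs on shared days.

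**Step 6: missing onset times.** Under the date-only fallback, every same-day event counts for the windowed terms, including one that began during the earlier cetuximab infusion. If the preferred term were simply brought under the window, it would inherit this.

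**The case against.** The exemption has a plausible rationale, although the SAP does not state it. A time window is a proxy needed for non-specific terms such as fever, whereas 'infusion related reaction' is already a diagnosis. The Phase 1b objective is the safety of the combination. Protocol 5.12 lists infusion reactions in cetuximab's toxicity profile and says NKTR-255 may enhance cetuximab's adverse effects. A Day 8 or Day 15 reaction is therefore relevant, and a row naming cetuximab as the cause would prejudge the question. This stands. It argues against merely deleting the exemption and for labelling rows by timing.

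There are also safeguards. The tables run by category and preferred term, so the term has its own row. Protocol 7.4 assesses causality for each drug. SAP 7.6.2 plans NKTR-255-related tables by system organ class and preferred term, an observations listing, and a listing of how events were categorised. The 48-hour wording sits in the SAP's category list, not in the table titles, so its appearance in the output is an inference. These points lower the weight of the issue. They do not supply the missing timing rule or remove the disagreement within the section.

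Three stronger readings may tempt a reader:
- That all cetuximab reactions before NKTR-255, including the Day -7 load and Cycle 1 Day 1, are counted. The NKTR-255 treatment-emergent period generally keeps these out of the tables. The exclusion is not watertight: SAP 6.6.1 treats any treatment-related event as treatment-emergent, SAP 6.6 includes cetuximab in study treatment, and Cycle 1 Day 1 needs an onset time. But the documents do not say that they are counted.
- That a given percentage of patients would be wrongly counted. No IRR rate appears in the documents, and a constant risk per infusion would be doubtful because Protocol 5.3.2 ends cetuximab after a Grade 3 or 4 reaction.
- That the primary endpoint is distorted. SAP 4.1 names the incidence of dose-limiting toxicities and of treatment-emergent adverse events; the exemption changes neither.

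**Conclusion.** The point holds as an internal inconsistency that misdescribes one safety category. As written, events coded to the preferred term on Days 8 and 15, or before that day's NKTR-255 from Cycle 2 onward, enter the three summaries without a causality filter, in a category defined as following NKTR-255 by at most 48 hours.

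The exposure is 11 of 13 planned cetuximab infusions over 4 cycles, 8 of them on cetuximab-only days. That count assumes full dosing and onset near the quoted median. It falls for responders who move to NKTR-255 alone, which the protocol allows after a tumour assessment. The first is due at 9 weeks, that is, after 9 ÷ 3 = 3 cycles, where the count is 8 of 10. It measures opportunities for miscounting and says nothing about how many events will occur.

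No design, dosing rule or primary endpoint is touched, and no event is lost from reporting. The change is still worth making, because the category cannot be read at face value and the correction is cheap.

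**What to change.** In SAP 7.6.2, state an explicit timing rule for the preferred term and make the category description agree with it. Then show the term in three rows:

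- **(a)** Onset from the start of an NKTR-255 infusion to 48 hours after.
- **(b)** Onset outside that window: on a cetuximab-only day, or on a shared day before NKTR-255 starts. Label this row by timing, not by cause.
- **(c)** Dosing-day events with no recorded onset time, shown as 'timing not separable' and not placed in row (a) by the date-only fallback.

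Keep every event with this term in the overall treatment-emergent adverse-event tables.

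The cost is SAP wording and minor programming; the SAP already plans to use onset time for the other terms in the category. Row (c) will be as large as the gaps in onset-time recording make it; the documents do not say how often time is captured. A footnote should say that rows (a) and (b) do not fully separate the drugs on shared days, because NKTR-255 follows the end of cetuximab by only 1 to 3 hours.
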